8.8.6. Other Events Endpoints

The number of hospitalization days during the study will be analyzed descriptively, and the incidence of patient hospitalizations will be analyzed using Fisher's exact test, for FAS at final analysis. Separate analyses will be presented for hospitalizations due to any reason and due to reasons related to the kidney.

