The number of hospitalization days during the double-blind period will be analyzed descriptively, and the incidence of patient hospitalizations analyzed using Fisher's exact test. Separate analyses will be presented for hospitalizations due to any reason and due to reasons related to the kidney (list to be determined prior to unblinding).

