3.2.3. Exploratory Endpoints

Exploratory endpoints for the double-blind period are:

- The slopes of eGFR over approximately 1 year of randomized treatment evaluated following the initial acute effect of randomized treatment (ie, from Week 6 to Week 60; chronic slope over 1 year) and after initiation of randomized treatment (ie, from Day 1 to Week 60; total slope over 1 year)
- The absolute and percent change from baseline of the double-blind period in eGFR at each visit
- The percent change from Week 6 in eGFR at each visit
- The proportion of patients achieving FPRE, defined as UP/C ≤ 1.5 g/g (170 mg/mmol) and a $>40\%$ reduction from baseline of the double-blind period in UP/C at each visit
- The percent change from baseline of the double-blind period in UP/C at each visit
- The time to achieve the target reduction in UP/C (ie, FPRE, as defined as ≤ 1.5 g/g [170 mg/mmol] and a $>40\%$ reduction)
- The proportion of patients reaching a confirmed 40% reduction in eGFR, end-stage renal disease (ESRD), or death. ESRD is defined as initiation of renal replacement therapy (RRT) or sustained eGFR <15 mL/min/1.73 m² during the study
- The proportion of patients reaching a confirmed 30% reduction in eGFR, ESRD, or death
- Changes from baseline of the double-blind period in blood pressure at each visit
- The proportion of patients requiring initiation of or intensification in immunosuppressive medication during the study
- The proportion of patients undergoing reduction in immunosuppressive medication during the study
- The time to initiation or intensification in immunosuppressive medication during the study
- Changes from baseline of the double-blind period in quality of life (QOL), measured via patient-reported outcome (PRO) at each visit beginning with Week 12
- Frequency and duration of hospitalizations (for any reason and for reasons related to the kidney)
- Trough plasma pharmacokinetic (PK) concentrations during the double-blind period

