4.3. Sample Size Considerations

4.3.1. Sample Size Justifications

Approximately 300 patients will be randomized and allocated 1:1 to receive sparsentan or irbesartan. This sample size takes into consideration enrollment feasibility in this rare disease setting and was evaluated using simulations.

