8.8.4. Other Responder Endpoints

The following responder endpoints will be summarized descriptively for FAS at both the interim and final analysis and compared (at final analysis only) between treatment groups using a CMH test controlling for the randomization variables:

- The proportion of patients reaching a confirmed 40% reduction in eGFR, ESRD, or death. ESRD is defined as initiation of RRT or sustained eGFR <15 mL/min/1.73² during the study (confirmed after repeat assessment of at least 14 days after initial assessment)
- The proportion of patients reaching a confirmed 30% reduction in eGFR, ESRD, or death
- The proportion of patients requiring initiation or intensification in immunosuppressive medication during the study
- The proportion of patients undergoing reduction in immunosuppressive medication during the study

Reduction of eGFR requires confirmation by a value at least 4 weeks after the initial value. If the last value on randomized treatment is the initial value for reduction or eGFR <15 mL/min/1.73² then the last value on randomized treatment is considered confirmed or sustained.

Initiation of RRT will be entered on the Concomitant Procedures eCRF as “chronic dialysis” or “kidney transplant” and on the Adverse Events eCRF as “progression of CKD leading to chronic dialysis” or “progression of CKD requiring kidney transplant”.

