8.8.9. Other Immunosuppressive Agent Endpoints

The following endpoints related to use of immunosuppressive agents will be analyzed for IAS at the time of interim analysis and FAS at final analysis and compared (at final analysis only) between treatment groups.

The number of days treated with immunosuppressive agents while on randomized treatment and the total number of episodes of immunosuppressive agent use while on randomized treatment will be analyzed using a negative binomial regression model, via PROC GENMOD in SAS. Specifically, the model will compare treatment groups, adjusted for the randomization stratification factors, and will include the natural log transformation of duration of exposure in the double-blind period as an offset term. Estimated event rates will be extracted from the model for each treatment. The treatment effect will be presented as the ratio of event rates, along with the associated 95% CI and 2-sided p-value.

The time to first post-baseline immunosuppressive agent use while on treatment in the randomized treatment period will be analyzed per Section 8.8.8. Patients with no on-treatment use of immunosuppressive agents will be censored at the time of analysis (if still on randomized treatment) or the time of discontinuation of randomized treatment, whichever is earlier.

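### Hospitalization frequency is a listed endpoint, but the plan compares only whether a patient was ever admitted, without using admission counts, time at risk or the randomization strata

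*SAP*

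**What the plan says.** SAP 3.2.3 lists the exploratory endpoint as "Frequency and duration of hospitalizations (for any reason and for reasons related to the kidney"; the protocol lists it in the same terms in 6.1.1.3.

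The analysis has two parts:

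- **Duration.** SAP 8.8.6: "The number of hospitalization days during the study will be analyzed descriptively".
- **Incidence.** SAP 8.8.6: "the incidence of patient hospitalizations will be analyzed using Fisher's exact test, for FAS at final analysis". Protocol 12.7.3 has "the incidence of patient hospitalizations analyzed using Fisher's exact test".

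Both parts are run for any-cause and for kidney-related admissions. Neither document specifies a count, rate or time-to-event model for hospitalization, a stratified test, or an exposure adjustment.

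The same SAP treats similar data differently. In 8.8.4 other patient proportions are "compared (at final analysis only) between treatment groups using a CMH test controlling for the randomization variables". In 8.8.9 days and episodes of immunosuppressive use "will be analyzed using a negative binomial regression model, via PROC GENMOD in SAS", adjusted for the randomization factors, and that model "will include the natural log transformation of duration of exposure in the double-blind period as an offset term".

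**The concern.** An endpoint called frequency and duration, followed for 112 weeks, would ordinarily yield a count of admissions and a rate. The planned test reduces each patient to admitted or not. A patient with one admission and a patient with five score the same. So do a patient lost at Week 4 without an admission and one followed to Week 112 without an admission.

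Three things are at stake:

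- The trial would give no between-arm estimate of how often patients are admitted.
- If treatment lowers the admission rate generally, information in repeat admissions is left unused.
- If follow-up differs between arms, the yes/no comparison tends to favour the arm that was observed for less time.

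The plan gives no reason why hospital admissions should be handled differently from the episodes and days in SAP 8.8.9.

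**Working it through.** **Inputs from the documents.** "Approximately 300 patients will be randomized and allocated 1:1 to receive sparsentan or irbesartan" (SAP 4.3.1), so 150 per arm. Two-sided 0.05 (protocol 12.10.1). Double-blind period of 112 weeks (protocol 6.2), or 112/52 = 2.154 years. The documents give no admission rate, effect size, dispersion, dropout rate or power for this endpoint, so there is no figure of the plan's own to reproduce.

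**Assumed inputs.** Control rate 0.1 to 0.5 per patient-year, rate ratio 0.5 to 0.8, negative binomial dispersion k from 0.01 to 4, and 20% dropout unless stated.

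**One case by hand.** Take control rate 0.30, rate ratio 0.6, k = 1 and no dropout.

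- Mean admissions per patient: 0.30 × 2.154 = 0.646 in control; 0.18 × 2.154 = 0.388 on treatment.
- Proportion ever admitted, 1 − (1 + kμ)^(−1/k): 1 − 1/1.646 = 39.3%; 1 − 1/1.388 = 27.9%.
- Rate model. Variance of the log rate ratio is the sum over arms of (1/μ + k)/150: (1.548 + 1)/150 + (2.579 + 1)/150 = 0.0409, SE 0.202. Then |ln 0.6|/SE = 0.511/0.202 = 2.53, and power is Φ(2.53 − 1.96) ≈ 71%.
- Two proportions, normal approximation. Difference 0.113, SE √(0.393×0.607/150 + 0.279×0.721/150) = 0.0541, ratio 2.09, and power is Φ(0.13) ≈ 55%.
- Simulation of the same case (600 trials, standard error about 2 points): negative binomial 71.7%, Fisher 48.7%. So about 16 of the 23 points come from reducing counts to yes/no, and about 6 from Fisher's conservatism.

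**Over the assumed range** (600 to 800 simulated trials per cell, 20% dropout):

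| Control rate/yr | Rate ratio | Negative binomial minus Fisher, points |
|---|---|---|
| 0.15 | 0.6 | +10 to +13 |
| 0.15 | 0.5 | +8 to +18 |
| 0.30 | 0.6 | +16 to +24 |
| 0.30 | 0.5 | +6 to +27 |
| 0.50 | 0.6 | +14 to +34 |
| 0.50 | 0.5 | +2 to +34 |
| 0.10 to 0.50 | 0.7 to 0.8 | +2 to +27 |

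**Fisher's conservatism alone.** Exact enumeration against Pearson chi-square at 150 per arm: 20% vs 10% gives 62.9% vs 68.6%; 30% vs 18% gives 64.1% vs 68.8%. Over the pairs tried the cost is about 4 to 6 points. At 20% in both arms Fisher's actual size is 3.6%.

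**Reversal.** Let treatment change only whether a patient is ever admitted, with clustered repeat admissions that treatment does not affect. At 30% vs 18% ever admitted, Fisher has 62 to 63% power and the negative binomial model 42 to 61%. At 40% vs 25% the figures are 75% and 51%. Fisher is 2 to 24 points better.

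**Unequal loss, equal true rates.** Assume exponential loss reaching 10% in one arm and 30% in the other by Week 112. The hazards are −ln(0.9)/2.154 = 0.0489 and −ln(0.7)/2.154 = 0.166 per year. Mean follow-up is 0.10/0.0489 = 2.04 and 0.30/0.166 = 1.81 years, about 11% less observation in one arm. In simulation, Fisher rejects about 5 to 12% of the time, least at 0.1 per year and most at 0.5. A rate test with robust standard error rejects about 4 to 6%.

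**The case against.** The strongest objection is to any flat statement of lost power. A reader might infer that Fisher's test costs this trial some fixed, large amount, because control rates of 0.2 to 0.5 and a rate ratio of 0.6 readily give gains above 15 points. The documents do not support that. They state no rate, effect or dispersion; at 0.10 to 0.15 per year the gain is mostly 2 to 18 points; and the sign reverses if the effect is confined to ever being admitted. Some of the gain is also Fisher's conservatism rather than lost information. This objection stands in full.

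Second, the protocol sometimes uses frequency for a number of patients (12.1, 12.5, 12.9.1), so patient incidence could be read as the intended frequency. That is arguable. It still leaves no comparison of admissions and no allowance for time at risk. Nor are event counts wholly absent: SAP 10.1 tabulates total entries of serious events by arm, and in-patient hospitalization makes an event serious (protocol 10.2). Those tables are descriptive, not specific to hospitalization and not exposure-adjusted.

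Third, a reader might infer that unequal follow-up already biases this comparison. Nothing in the documents shows that. The 10% vs 30% loss is an assumption, and protocol 6.4.2 encourages patients who stop study drug to continue visits to Week 112. An offset also does not cure informative loss, and a CMH test of ever-hospitalized ignores time at risk just as Fisher's test does.

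**Conclusion.** The point holds on the text. The listed endpoint is frequency and duration; the only between-arm test is an unstratified yes/no comparison; and the SAP's own methods in 8.8.4 and 8.8.9 use the strata and, for counts, exposure time.

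The size is conditional. If treatment scales the admission rate, a rate model gains roughly 2 to 34 points over Fisher's test across the assumed range. If treatment affects only whether a patient is ever admitted, it can lose 2 to 24. Protection against unequal follow-up matters only if such an imbalance arises and loss is not informative.

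The importance is low. The endpoint is exploratory, no power is claimed for it, and it lies outside the testing hierarchy in SAP 8.4. This is an inexpensive improvement, and no confirmatory conclusion depends on it.

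**What to change.** In SAP 8.8.6 and protocol 12.7.3:

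- Add a comparison of the number of admissions per patient in the double-blind period, following the form of SAP 8.8.9: negative binomial, or Poisson with robust standard error, with treatment and randomization strata. Report the rate ratio and 95% CI separately for all-cause and kidney-related admissions.
- Use log double-blind follow-up time as the offset, so that it matches the period over which admissions are counted. The exposure offset in 8.8.9 suits events counted on treatment only.
- Keep the proportion ever hospitalized as a supportive comparison, using the stratified CMH test of SAP 8.8.4. Hospital days can stay descriptive.
- Align the period: SAP 8.8.6 refers to the study and protocol 12.7.3 to the double-blind period. SAP 8.1 already limits efficacy analyses to the latter.

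The cost is a wording change and one extra model on data already collected. The downside is that the rate comparison can be less powerful than the yes/no test if the effect is only on first admission; keeping the supportive comparison covers that case.

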8.8.7. Other Categorical Endpoints

Shifts in EQ-5D-5L and EQ-5D-Y health states from baseline to worst value (scheduled or unscheduled), last value (scheduled or unscheduled), and at each scheduled post-baseline visit will be provided by treatment group for FAS at final analysis.

8.8.8. Other Time-to-Event Endpoints

For the time-to-event analyses, patients who do not experience an event will be censored at the time of analysis (if still on randomized treatment) or the time of randomized treatment discontinuation (whichever is earlier). Treatment groups will be compared using a log rank test stratified by the randomization stratification variables for FAS at both interim and final analysis. KM estimates of the distribution of the time-to-event will be tabulated and graphed by treatment group. The tabulation will include the KM estimate of the medians and corresponding 95% CIs, if the medians can be estimated.

8.8.9. Other Immunosuppressive Agent Endpoints

The following endpoints related to use of immunosuppressive agents will be analyzed for IAS at the time of interim analysis and FAS at final analysis and compared (at final analysis only) between treatment groups.

The number of days treated with immunosuppressive agents while on randomized treatment and the total number of episodes of immunosuppressive agent use while on randomized treatment will be analyzed using a negative binomial regression model, via PROC GENMOD in SAS. Specifically, the model will compare treatment groups, adjusted for the randomization stratification factors, and will include the natural log transformation of duration of exposure in the double-blind period as an offset term. Estimated event rates will be extracted from the model for each treatment. The treatment effect will be presented as the ratio of event rates, along with the associated 95% CI and 2-sided p-value.

The time to first post-baseline immunosuppressive agent use while on treatment in the randomized treatment period will be analyzed per Section 8.8.8. Patients with no on-treatment use of immunosuppressive agents will be censored at the time of analysis (if still on randomized treatment) or the time of discontinuation of randomized treatment, whichever is earlier.

9. PHARMACOKINETICS

The PK Analysis Set will be used for all PK analyses. Trough plasma levels of study medication will be summarized at both interim and final analysis with descriptive statistics over time by treatment group, including the geometric mean and geometric CV%. Analyte concentrations below the lower limit of quantification will be indicated by BLQ (below limit of quantitation) and set to missing. However, the number of BLQs at each time point will be provided in the summary table.

10. SAFETY AND TOLERABILITY

Safety analyses will be conducted using the Safety Analysis Set at both interim and final analysis. At the interim analysis, all available data will be summarized. Unless otherwise noted, all safety analyses will be conducted using on-study data. All safety analyses specified below refer to the double-blind period only, except where noted. If >5% of patients initiate RRT while on study, select summaries excluding results after initiation of RRT may be prepared.

10.1. Adverse Events

Adverse event (AE) data will be collected from the time that signed informed consent is obtained until the patient fully completes his/her participation in the study.

All AE summaries will be restricted to TEAEs, which is defined as any AE that newly appears, increases in frequency, or worsens in severity following the initiation of study medication. If it cannot be determined whether the AE is treatment emergent due to a partial onset date, then it will be counted as treatment emergent. Verbatim terms will be coded to PT and SOCs using MedDRA.

Each AE summary will be displayed by treatment group. Summaries that are displayed by SOC and PT will be ordered by descending order of incidence of SOC and PT within each SOC. Summaries of the following types will be presented:

- Overall summary of TEAEs
- Patient incidence of TEAEs and the total number of entries by SOC and PT
- Patient incidence of TEAEs and the total number of entries by PT in descending order
- Patient incidence of TEAEs by SOC, PT, and highest severity. At each level of patient summarization, a patient is classified according to the highest severity if the patient reported 1 or more events. AEs with missing severity will be considered severe for this summary.
- Patient incidence and total number of entries of severe TEAEs by SOC and PT. AEs with missing severity will be considered severe for this summary.
- Patient incidence of TEAEs by SOC, PT, and closest relationship to study medication (Related/Not Related). Related AEs are those with relationships reported as “Possibly Related” or “Related” and unrelated AEs are those with relationships reported as “Unlikely Related” or “Not Related.” At each level of patient summarization, a patient is classified according to the closest relationship to study medication if the patient reported 1 or more events. AEs with a missing relationship will be considered related for this summary.
- Patient incidence and total number of entries of related TEAEs by MedDRA SOC and PT. AEs with a missing relationship will be considered related for this summary.
- Patient incidence of serious TEAEs and the total number of entries by SOC and PT
- Patient incidence of TEAEs leading to treatment discontinuation by SOC and PT
- Patient incidence and total number entries of treatment-emergent adverse events of interest (AEOIs) by SOC and PT

- Patients incidence and total number of entries of TEAEs associated with safety topics of interest by PT
- Patients incidence and total number of entries of related TEAEs associated with safety topics of interest by PT
- Patients incidence and total number of entries of serious TEAEs associated with safety topics of interest by PT

10.1.1. Adverse Events of Interest

Abnormal liver function tests that meet the below criteria are considered AEOIs:

- The abnormality represents new elevation in alanine aminotransferase (ALT) or aspartate aminotransferase (AST) >3 times the upper limit of normal (ULN), with or without an elevation of total serum bilirubin >2 times ULN
- The abnormality represents a 2-fold increase in ALT or AST above the baseline value in patients who had elevated values prior to starting study medication.

As described in [Section 10.1](#), patient incidence of treatment-emergent AEOIs will be summarized by treatment group.

In order to explore the relationship between liver function abnormalities and study medication, the following time-to-event analysis will be performed:

- Time to first onset of treatment-emergent AEOI
 - The time to the start of the first occurrence will be calculated by the date of onset of first AEOI – date of first dose of study medication + 1
 - Patients who never reported an AEOI will be censored at the date of completion or discontinuation in randomized treatment period or data cut-off date of analysis, whichever is earlier
- Time to resolution of the most severe treatment-emergent AEOI
 - If multiple treatment-emergent AEOIs with the same preferred term with increasing severity were reported for the same patient, the time to resolution will be calculated by the date of resolution of the most severe event – start of the initial event + 1
 - Otherwise, the time to resolution will be calculated by the date of resolution of the event – start of the event + 1
 - Patients whose most severe treatment-emergent AEOI is ongoing will be censored at the date of completion or discontinuation in randomized treatment period or data cut-off date of analysis, whichever is earlier
 - Only patients who had reported a treatment-emergent AEOI are included in this analysis.

The analysis of time to event will include the number of patients with, the number of patients without event (censored), descriptive statistics of time for those with an event, and range in days for all patients. KM estimates will be calculated by treatment group. The quartiles, including the

median time-to-event and their respective 2-sided 95% CIs, will be presented. KM estimates will be plotted as a cumulative probability plot for each treatment group, with the number at risk identified.

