10.3. Adverse Events of Interest (AEOI)

10.3.1. Abnormal Liver Function Test Results

Abnormal liver function tests that meet the below criteria will be considered AEOIs and must be reported to the Sponsor's Medical Monitor within 24 hours of awareness if one of the following conditions are met:

- The abnormality represents a new elevation in ALT or AST >3 times the upper limit of normal (ULN), with or without an elevation of total serum bilirubin >2 times ULN; or
- The abnormality represents a 2-fold increase in ALT or AST above the baseline value for the double-blind period (ie, Day 1) in patients who had elevated values prior to starting study medication, or a 2-fold increase in ALT or AST above the baseline value for the open-label extension (ie, Week 112) in patients who had elevated values prior to starting open-label sparsentan.

In such instances, the following steps should be taken:

1. Temporarily discontinue study medication.
2. Perform repeat testing of ALT, AST, and total bilirubin, and test liver alkaline phosphatase isoenzyme within 48 to 72 hours to confirm the abnormalities.
3. If the abnormality is confirmed by repeat results:
 - a. Complete an AEOI Report Form that documents both the liver function test findings and any associated signs or symptoms and report by email to the SAE contact on the [Study Contact Information](#) page of this protocol.
 - b. Monitor liver enzymes and serum bilirubin 2 or 3 times weekly. The frequency of re-testing can decrease to once weekly or less if the abnormalities stabilize and the patient is asymptomatic.

- c. Perform additional testing to evaluate liver function, as appropriate (eg, international normalized ratio [INR], direct bilirubin).
4. Do not resume study medication until monitoring indicates abnormalities have resolved or stabilized.

Patients are not allowed to resume study medication if they have:

- ALT or AST >8 times ULN
- ALT or AST >5 times ULN for more than 2 weeks
- ALT or AST >3 times ULN and total bilirubin >2 times ULN or INR >1.5
- ALT or AST >3 times ULN with symptoms of fatigue, nausea, vomiting, right upper quadrant pain or tenderness, fever, rash and/or eosinophilia (>5% eosinophils)

Additionally, patients who demonstrate elevated liver enzymes a second time after re-introduction of the study medication may continue in the clinical trial; however, they will not receive study medication for the remainder of the trial.

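### Time to resolution of the worst liver event is counted from the patient's first event even if that event had resolved, so a higher-grade recurrence after restart absorbs the event-free gap

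*SAP*

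**What the plan says.** SAP 10.1.1 defines two time-to-event analyses for liver AEOIs. The second is headed "Time to resolution of the most severe treatment-emergent AEOI". It has two timing rules.

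- **Special rule.** The trigger is "If multiple treatment-emergent AEOIs with the same preferred term with increasing severity were reported for the same patient". The time is then "date of resolution of the most severe event – start of the initial event + 1".
- **All other cases.** "Otherwise, the time to resolution will be calculated by the date of resolution of the event – start of the event + 1".

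The trigger has three conditions: one patient, one preferred term, rising severity. It does not ask whether the earlier event had ended. Only patients with a treatment-emergent AEOI enter the analysis. Output by arm is descriptive statistics, the range, and Kaplan-Meier quartiles with confidence intervals.

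Protocol 10.3.1 sets out what follows a qualifying liver abnormality. The first step is "Temporarily discontinue study medication". A later step is "Do not resume study medication until monitoring indicates abnormalities have resolved or stabilized". The section then provides for "patients who demonstrate elevated liver enzymes a second time after re-introduction of the study medication", who may stay in the trial but receive no further study drug.

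Neither document defines an episode, and neither confines the first event to the same continuous episode as the most severe one.

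**The concern.** The rule suits one worsening event that has been entered as several records of rising grade. As written, it also covers two separate events with a documented recovery between them, and there it counts healthy days and the drug restart as unresolved liver injury.

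The protocol's own pathway can produce that pattern. Restart is barred after the more marked abnormalities, so restarted patients are those whose first episode fell short of those limits, and a higher-graded second episode is plausible. SAP 6.6.5 also treats missing severity as severe, so an ungraded second record can trigger the rule.

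At stake is how patients with a recurrence after restart are described. SAP 10.1.1 says the analysis is meant to explore how liver abnormalities relate to study drug, and these patients are informative for that purpose. Two short reversible episodes reported as one long one obscure both the reversibility and the recurrence.

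**Working it through.** The documents give no figure to reproduce here, so the check applies the SAP's date formulas directly.

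**Inputs from the documents**
- The two timing formulas: SAP 10.1.1.
- Hold, restart and second elevation: Protocol 10.3.1.
- Blinded treatment of 108 weeks (756 days), which bounds the gap, and visits every 12 weeks (84 days) after Week 12: SAP 4.1.
- Days per month, 365.25/12: SAP 6.5.3.

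**Assumed, not in the documents**
- Episode lengths L1 and L2, equal, at 14, 21 or 28 days.
- Event-free gap g, from 0 to 600 days.

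**Formulas**
- Special rule: end of second event − start of first event + 1 = L1 + g + L2.
- Second event's own time: end − start + 1 = L2.
- Excess: L1 + g.

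**Worked case.** First episode Days 43–63 (21 days, resolved), 84 event-free days, then a higher-grade episode with the same preferred term on Days 148–168.
- Special rule: 168 − 43 + 1 = 126 days (126/30.4375 = 4.1 months).
- Own episode: 168 − 148 + 1 = 21 days.
- Ratio: 126/21 = 6.

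**Range for 21-day episodes**

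| Gap (days) | Special rule (days) | Own episode (days) |
|---|---|---|
| 0 | 42 | 21 |
| 14 | 56 | 21 |
| 28 | 70 | 21 |
| 84 | 126 | 21 |
| 168 | 210 | 21 |
| 336 | 378 | 21 |
| 600 | 642 | 21 |

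At gap 0 the 42 days are right: they are the length of one continuous episode split into two records. At an 84-day gap, 14-day episodes give 14 + 84 + 14 = 112 days and 28-day episodes give 28 + 84 + 28 = 140.

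**Consistency check.** Keep the same dates, but let the second event have the same or a lower grade than the first. Severity is no longer rising, so the other rule applies and the event analysed runs from its own start to its own end. Both events last 21 days, so the result is 21 days whichever one is used. Two patients with identical dates therefore get 126 and 21 days solely because of how the first episode was graded.

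**Effect on a small set (assumed).** Six patients in one arm, all resolved, have own-episode times of 14, 18, 21, 21, 25 and 30 days. Replace one 21 by 126.
- Mean: 129/6 = 21.5 becomes 234/6 = 39.0.
- Upper quartile (first time the unresolved proportion falls below 0.25): 25 becomes 30.
- Maximum: 30 becomes 126.
- Median: 21 stays at 21, or becomes 23 if the midpoint of the flat step between 21 and 25 is taken.

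**The case against.** The best defence is that the rule was written for a single worsening event split across records. For that case it is correct, as the gap-0 row shows. This stands, and any fix should preserve it. But the text does not limit the rule to that case, and the protocol describes the other.

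The affected group is also narrow. A patient needs a first event that truly resolved, a permitted restart, and a second event with the same preferred term and a higher grade. Restart is also allowed after mere stabilization, and the first event's start is then the right origin. This stands too: it limits how many patients are affected but does not make the rule right for those who qualify.

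Third, other hepatic outputs are untouched: multiples of the upper limit of normal with the hepatotoxicity plots (SAP 10.4.3), toxicity-grade shifts (SAP 10.4.2) and hepatic event summaries (SAP 10.1.2). By-patient listings should show the two events separately. That limits the harm, but the Kaplan-Meier summary would still be wrong for those patients.

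A reader might also infer that the rule can err the other way, cutting a time short when a falling grade is entered as a new record. The documents do not support this. They do not say that improvement is recorded that way, Protocol 10.6.3 keeps resolving separate from resolved, and the SAP 10.1 definition of a treatment-emergent event covers new, more frequent or worse events, not improving ones.

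**Conclusion.** The point holds in limited form. For a recurrence of the same preferred term at a higher grade, after the earlier event had resolved, the stated rule overstates resolution time by the first episode plus the event-free gap. The defect is a missing qualifier in an otherwise sensible rule.

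The size rests on assumed dates: 126 days instead of 21 at an 84-day gap, and 56 to 642 days instead of 21 across gaps of 14 to 600 days. The documents give no AEOI count, durations or gaps, so the number of patients affected is unknown and may be none.

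A reader might infer that resolution times will generally come out in months instead of weeks, that several patients per arm will shift the median, or that the trial's conclusions on liver safety are compromised. None of these follows. The inflation depends on the gap, nothing suggests that many patients will meet every condition, and the analysis is exploratory with no hypothesis test resting on it. What does follow is that one qualifying patient in a small set can move the mean, upper quartile and range. That is reason enough for a one-line correction.

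**What to change.** In SAP 10.1.1, use the first event's start only when that event had not resolved, by its recorded outcome and end date, before the more severe record began. Otherwise time the most severe event from the start of its own episode and treat the recurrence as a new episode. Listing recurrences after re-introduction separately would keep that information visible.

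Resolution should be judged from the recorded outcome and end date, not from a requirement that records be no more than a day apart. Protocol 10.3.1 has retesting two or three times a week, falling to weekly or less, so a strict adjacency test could split one continuous episode.

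The cost is one or two sentences in the SAP and a small change to the derivation. It needs no new data and changes no confirmatory analysis and no patient management.
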